## 10.4. Exclusion Criteria

**Subjects will be excluded from enrollment in the study if they meet any of the following criteria:**

1. Subject is undergoing emergency surgery, i.e. lifesaving procedures performed where subject is in imminent danger of death.
2. Subject for which the device is used outside the product IFU, including:
  - a. Pregnant women: Women who are known or suspected to be pregnant, or who are planning to become pregnant during the study follow-up period
  - b. Subject who has an infection within 30 days of enrollment or, or at the time of the surgery, has any active, acute or chronic infection(s) that are uncontrolled and/or requiring treatment such as antibiotics
  - c. Subject whose surgical site is contaminated or dirty/infected intraoperatively, as assessed by the Investigator (Exclude Altemeier classification III-IV)
3. Subject who had received a mesh in a previous ventral hernia repair or has a ventral hernia.
4. Investigator determined that a planned future surgery would interfere with application of mesh reinforcement.
5. Subject has participated in an investigational drug or device research study within 30 days of enrollment.
6. Subject has a life expectancy of <2 years.
7. Subject has an ASA Physical Status Classification System score >3.
8. Subject has > 5 total risk factors or > 2 high-risk factors.

## 11. Study Procedures

### 11.1 Schedule of Events

Subjects will be evaluated at screening/baseline, procedure, Day 1, discharge, Day 8, and 1, 12, and 24 months post-surgery. Refer to Section 11.2 for procedure/assessments collected at each visit.

### 11.2 Data Collection

Table 2: Schedule of Events

Procedure/Assessment	Screening (Day -30 to 0)	Operative (Day 0)	Post-operative course (Day 0) Follow up	Post-operative course (Day 1) Follow up	Discharge Assessment	Post-operative course (Day 8, +/-2days) Follow Up	1 Month (Day 30, +/-1week) Follow-up	12 Months (-1/+4 weeks) Follow-up	24 Months (-1/+4 weeks) Follow-up
	Can be combined								
Eligibility criteria	X 	X 							
Informed consent	X 								
Pregnancy Test	X 								
Subject demographics	X								
Relevant prior medical/surgical history	X								
Surgical Data									
Date of surgery		X							
Procedure indication		X							
Surgical technique for laparotomy closure		X							
Mesh reference and lot number		X							
Type of fixation		X							
Operative time		X							

# ProGrip Self-Gripping Polyester Mesh (POETRY)

## Clinical Investigation Plan

MDT17048POETRY

Version 4 – 25 Sep 2020

Page 28 of 72

Medtronic

Procedure/Assessment	Screening (Day -30 to 0)	Operative (Day 0)	Post-operative course (Day 0) Follow up	Post-operative course (Day 1) Follow up	Discharge Assessment	Post-operative course (Day 8, +/-2days) Follow Up	1 Month (Day 30, +/-1week) Follow-up	12 Months (-1/+4 weeks) Follow-up	24 Months (-1/+4 weeks) Follow-up
	Can be combined								
Mesh positioning and time		X							
Peri-operative events (including adverse device effects or procedure related adverse events)		X							
Surgeon satisfaction		X							
Post-operative data									
AE, SAE, & DD Data			X	X	X	X	X	X	X
VAS pain assessment 			X	X		X	X	X	X
Post-operative adverse events				X	X		X	X	X
Date of discharge					X				
Length of Hospital stay					X				
Physical exam including hernia clinical examination 							X	X	X
Abdominal CT Scan 								X	X
Quality of Life Questionnaire 							X	X	X
Patient Satisfaction 								X	X
1-month prior phone call including self-assessments 								X	X
Study Exit									X
1. If Screening and Surgery occur on different days, these procedures should occur during Screening and be reconfirmed on the day of surgery. 2. No study procedures will be performed until informed consent form has been completed. Subject should be re-consented if date of original consent is greater than 30 days. 3. Serum or urine pregnancy test for female subjects (unless the patient is surgically sterile or postmenopausal for at least two years). 4. These procedures/assessments may not be considered standard of care based upon local standards or index procedure type									

## 11.3 Scheduled Follow-up Visit Windows

Should a subject miss a visit or the visit fall outside the pre-specified window, a study deviation must be reported, and the original follow-up schedule maintained for subsequent visits.

Data analyses include follow-up visits, regardless of whether the visit occurs within the window. Therefore, a late visit is preferred over a missed visit but must be accompanied by a deviation report. Follow-up visit windows are listed in Table 3 and are based on days post-operative.

**Table 3: Data collection and study procedure requirements at subject visits**

Study Follow-up Visit	Window (Calculated days post-operative)		
	Window Start (post-implant)	Target (post-implant)	Window End (post-implant)
Follow-up 1	Day 6	Day 8	Day 10
Follow-up 2	Day 23	Day 30	Day 37
Follow-up 3	11 Months, 3 Weeks	12 Months	13 Months
Follow-up 4	23 Months, 3 Weeks	24 Months	25 Months

## 11.4 Subject Screening

A screening visit will be used to confirm pre-operative eligibility and consent subjects. Subjects will be consented prior any procedures specific to the study are undertaken. The purpose and all aspects of the study will be explained to the subject. Subjects who agree to study participation must sign and personally date the sponsor and an EC-approved informed consent form prior to participating in any study activities.

Once the consent process has been completed, pre-operative eligibility has been confirmed, the following data will be collected:

- Demographic data (e.g. age, gender, ASA score, BMI, subject's occupation)
- Relevant prior medical/surgical history (e.g. previous surgical procedure)
- Serum or urine pregnancy test, for female subjects (unless the patient is surgically sterile or postmenopausal for at least two years).

The screening visit will be performed within 30 days up to the day of the scheduled procedure and may be combined with the surgery procedure visit. If screening and/or ICF signature occur more than 30 days before the procedure the subject is to be rescreened and reconsented.

## 11.5 Subject Consent

Informed consent is defined as a legally effective documented confirmation of a subject's voluntary agreement to participate in a particular study after information has been given and explained to the subject on all aspects of the study that are relevant to the subject's decision to participate. This process includes obtaining an IC form that has been approved by the study site's EC and signed and dated by the subject. A subject may only consent after information has been given and explained to the subject on all aspects of the clinical investigation that are relevant to the subject's decision to participate.

Prior to enrolling subjects, the IC site must be approved by the EC. The document(s) must be controlled (i.e. versioned and/or dated) to ensure it is clear which version(s) were approved by the EC. Any adaptation of the sample IC must be reviewed and approved by Medtronic and the EC reviewing the application prior to enrolling subjects.

The investigator must notify the subject of any significant new findings about the study that become available during the course of the study which are pertinent to the safety and well-being of the subject, as this could impact a subject's willingness to participate in the study. If relevant, consent may be requested from subjects to confirm their continued participation.

Prior to initiation of any study-specific procedures, IC must be obtained from the subject. Likewise, privacy or health information protection regulation may require subjects to sign additional forms to authorize study sites to submit subject information to the study sponsor. The IC process must be conducted by the principal investigator or an authorized designee, and the IC Form and must be given to the subject in a language he/she is able to read and understand. The process of IC must be conducted without using coercion or undue improper influence on or inducement of the subject to participate by the investigator or other study site personnel. The IC process shall not waive or appear to waive subject's legal right. The language used shall be as non-technical as possible and must be understandable to the subject.

The subject must have ample time and opportunity to read and understand the IC form, to inquire about details of the study, and to decide whether or not to participate in the study. All questions about the study should be answered to the satisfaction of the subject.

When the subject decides to participate in the study, the IC must be signed and personally dated by the subject and investigator or authorized designee, as required by the IC, and ensured by the principal investigator or his/her authorized designee.

If the IC is obtained the same day the subject begins participating in study-related procedures, it must be documented in the subject's case history that consent was obtained prior to participation in any study-related procedures. It is best practice for the IC process to be documented in the subject's case history, regardless of circumstance. The date the subject signed the IC and Data Protection Authorization, as required by law, must be documented in the subject's medical records.

The original of the signed IC must be filed in the hospital/clinical chart and/or with the subject's study documents.

The IC must be available for monitoring and auditing. Any Medtronic Field personnel who support the study procedure must be able to review the subject's signed and dated IC and verify its completeness prior to proceeding with the implant. In the event the Medtronic Field personnel identify IC as being incomplete, the study procedure will not be allowed to occur until the consent of the subject can be adequately and appropriately obtained.

A log of all subjects enrolled in the study should be maintained. Enrollment can be a stand-alone visit or can occur on the same day as the screening visit or operative day. Once consent is obtained, report adverse events/deaths, study deviations and subject exits as they occur.

## **11.6 Operative Day (D0)**

The following information is required to be collected on the operative day:

- Date of surgery
- Indication of the procedure
- Surgical technique for laparotomy closure (closure technique and type of suture)
- Mesh reference (TMP1509G, TMP1515G, TMP2015G, TMP3015G, TMP1008G, TMP2008G, TMP3008G, TMP4008G) and lot number
- Type of fixation
- Operative time (from incision to closure, skin to skin),
- Mesh positioning and time
- Peri-operative events including adverse device effects or procedure related adverse events
- Surgeon satisfaction (Club Hernie questionnaire regarding surgeon satisfaction of mesh handling, mesh manipulability, ease of use)

## **11.7 Scheduled Follow-up Visits**

### **11.7.1 Post-operative course (D0) Follow up**

The following information is required to be collected post-operatively on the operative day:

- Post-operative pain assessment measured utilizing a 0-10 Visual Analog Scale (VAS) (Worst pain experienced over the last 24 hours).

### **11.7.2 Post-operative course (D1) Follow up**

The following information is required to be collected during post-operative day 1:

- Pain assessment measured with VAS score
- Post-operative adverse events (including adverse device effects or procedure related adverse events: SSI, hematoma, seroma, etc.). Data will be recorded in the discharge data.

**11.7.3 Discharge Data**

The following information is required to be collected during discharge:

- Date of discharge
- Length of Hospital stay (number of nights in the institution after the surgery)
- Post-operative adverse events (including adverse device effects or procedure related adverse events: SSI, hematoma, seroma, etc.)

**11.7.4 Post-operative course, Day 8, (-/+2days) Follow up**

The following information is required to be collected during the Day 8 post-operative follow up (-/+ 2 days):

- Pain assessment measured with VAS score, either during systematic clinical visit or by phone call when a subject is already discharged.

**11.7.5 Post-operative course, Day 30, (-/+1 week) Follow up**

The following information is required to be collected during the Day 30 post-operative follow up (-/+ 1 week):

- Pain assessment measured with VAS score
- Physical exam including hernia clinical examination
- Post-operative adverse events (including adverse device effects or procedure related adverse events).
- Club Hernie Registry Quality of Life (QoL) Questionnaire

**11.7.6 Post-operative course, 12 Months, (-1/+4 week) Follow up**

The following information is required to be collected during the 12 Months post-operative follow up (-1/+4 weeks):

- Physical exam including hernia clinical examination
- Abdominal CT-Scan
- Post-operative adverse events (including adverse device effects or procedure related adverse events)
- Club Hernie Registry Quality of Life (QoL) Questionnaire and patient satisfaction
- Pain assessment measured with VAS score

NOTE: 1 Month prior, all subjects will be contacted by phone in order to complete a self-assessment questionnaire and to remind them of the 1-year follow-up visit.

**11.7.7 Post-operative course, 24 Months, (-1/+4 week) Follow up**

The following information is required to be collected during the 24 Months post-operative follow up (-1/+4 weeks):

- Physical exam including hernia clinical examination

- Abdominal CT-Scan
- Post-operative adverse events (including adverse device effects or procedure related adverse events)
- Club Hernie Registry Quality of Life (QoL) Questionnaire and patient satisfaction
- Pain assessment measured with VAS score

NOTE: 1 Month prior, all subjects will be contacted by phone in order to complete a self-assessment questionnaire and to remind them of the 2-year follow-up visit.

### 11.7.8 End of Study

After the 24-month follow-up no additional study related medical care will be provided, and subjects will receive the standard of care as determined appropriate by their physician.

If the ProGrip™ Self- gripping polyester mesh is removed from the subject, they will be exited from the study 30 days after mesh removal.

### 11.8 Subject Questionnaires

During this study the Visual Analog Scale (VAS) will be used to measure subject pain. VAS is a psychometric response scale, first used by Hayes and Patterson in 1921 (1, 2) and currently referenced in more than 950 published manuscripts. Scores are based on self-reported measures of symptoms that are recorded with a single handwritten mark placed at one point along the length of a 10-cm line that represents a continuum between the two ends of the scale, “no pain” on the left end (0 cm) of the scale and the “worst pain” on the right end of the scale (10 cm), which can be used in questionnaires to determine how much pain a subject is feeling.

The Club Hernie Quality of Life and Patient Satisfaction Survey will be used to determine how satisfied a subject is with the mesh placement and what impact it has had on their quality of life. Along with the Surgeon Satisfaction Questionnaire, the Club Hernie Quality of Life and Patient Satisfaction Surveys used in this study were developed by Club Hernie and have been in use in their database since 1999. To date, these questionnaires have been published in numerous manuscripts (3-9), including a recent Medtronic sponsored study (10).

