7.9. Evaluation of Objectives

Primary Objective and Endpoint

The primary objective of this investigation is to confirm the efficacy of ProGrip™ Self-gripping Polyester Mesh to reduce the incidence of incisional hernia within 24 months post-operatively in subjects undergoing procedure with midline laparotomies.

The primary endpoint is the incisional hernia rate within 24 months of midline laparotomy assessed by CT-scan and physical examination including hernia clinical examination.

Statistical analysis of primary endpoint will be comparative. Binomial one-way test will be used to compare the observed ProGrip™ Self- gripping Polyester Mesh incisional hernia incidence rate to the 20% theoretical incidence rate (from no prevention population), using a two- sided alpha-level of 5%.

Primary endpoint will be measured using Performance Analysis Set; a confirmatory analysis of primary endpoint will be run using Per Protocol Analysis Set.

Secondary objective and endpoints

The secondary objective of this investigation is to confirm the safety of ProGrip™ Self-gripping Polyester Mesh through the occurrence of adverse device effects or procedure related adverse events following the use of ProGrip™ Self-gripping Polyester Mesh in subjects undergoing procedures with midline laparotomies.

To confirm the safety of ProGrip™ Self-gripping Polyester Mesh through the occurrence of adverse device effects or procedure related adverse events following the use of ProGrip™ Self-gripping Polyester Mesh in subjects undergoing procedures with midline laparotomies.

The following secondary endpoints will be assessed:

- Adverse event (AE) incidence reported by number, severity, seriousness and relationship to the procedure and device from the surgery to the 24-month visit: AE incidence will be measured on Safety Analysis Set.
- Time to incisional hernia occurrence: will be measured using Kaplan Meier estimates, and based on SAS, and PPAS.
- Post-operative pain at the site of surgery: will be measured on SAS and PPAS, at each postoperative timepoint: Day0 (after surgery), Day1, Day8, Day30, Month12 and Month24.
- Quality of life: will be measured on all, PAS, SAS, and PPAS, using Club Hernie QOL questionnaire, combining qualitative and quantitative data, at Month1, Month12 and Month24.
- Patient satisfaction: at 12 then 24 months, measured on PAS, PPAS and SAS
- Surgeon satisfaction, measured on PAS, SAS, and PPAS

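### With no pre-operative pain or quality-of-life measure and no comparator, later scores describe post-operative levels but not impact; the Day 0 recall window and Day 8 pain mode also need repair.

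*Protocol*

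**What the plan says.** **Purpose.** Protocol 11.8 says of the Club Hernie quality-of-life and satisfaction survey that it "will be used to determine how satisfied a subject is with the mesh placement and what impact it has had on their quality of life".

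**Screening.** Protocol 11.4 lists "Demographic data (e.g. age, gender, ASA score, BMI" and occupation, then relevant history and a pregnancy test. It lists no pain score and no quality-of-life questionnaire, and the screening columns of Table 2 and of the schedule in SAP section 5 contain neither.

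**Follow-up.** SAP 7.9 measures pain "at each postoperative timepoint: Day0 (after surgery), Day1, Day8, Day30, Month12 and Month24". It measures quality of life by the Club Hernie questionnaire, "combining qualitative and quantitative data, at Month1, Month12 and Month24". Protocol 15.4.2 and SAP 7.2 make both descriptive, and no change from baseline is planned. Protocol 7.2 states that there is no comparator.

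**Day 0.** Protocol 11.7.1 opens with "The following information is required to be collected post-operatively on the operative day". The item is "Post-operative pain assessment measured utilizing a 0-10 Visual Analog Scale (VAS) (Worst pain experienced over the last 24 hours".

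**Day 8.** Protocol 11.7.4 specifies "Pain assessment measured with VAS score, either during systematic clinical visit or by phone call when a subject is already discharged". Section 11.8 describes the VAS score as "recorded with a single handwritten mark placed at one point along the length of a 10-cm line".

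**The concern.** A statement about impact needs something to compare with: the subject's own earlier state, or a group without the mesh. The plan has neither for quality of life. The eligibility criteria make pre-existing impairment plausible in part of the sample, since current or recent cancer, prior open abdominal surgery, aortic aneurysm and BMI of 35 or more all count as risk factors. None is compulsory: a subject can qualify on two low-risk factors alone.

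Pain has the same gap. Chronic pain is a listed risk in protocol 12.1, yet a subject who reports pain at 12 or 24 months has no earlier score to compare it with.

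Two narrower problems concern the pain series only. The Day 0 item is labelled post-operative but its recall period starts before the operation. The Day 8 item permits a mode that does not fit the description of the instrument, and the mode depends on whether the subject has gone home, which may itself be related to recovery.

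At stake is what can be reported from two of the six secondary endpoints.

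**Working it through.** **1. The plan's own figures.** The documents give no sample size or precision target for pain or quality of life. The only sizing is for the hernia endpoint (protocol 15.6, SAP section 6): 20% against 10%, two-sided 5%, 80% power.

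n = [(1.960 × √(0.20 × 0.80) + 0.842 × √(0.10 × 0.90)) / 0.10]² = 107.4, rounded up to 108; 108 / 0.80 = 135.

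Both stated figures reproduce, and nothing below touches them.

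**2. Count of pre-operative assessments.**

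| Measure | Scheduled time points | Before surgery |
|---|---|---|
| Pain VAS | Day 0 (after surgery), Day 1, Day 8, Day 30, Months 12 and 24 | 0 of 6 |
| Quality of life | Months 1, 12 and 24 | 0 of 3 |

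The protocol and the SAP agree, so the SAP does not supply what the protocol lacks.

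**3. What the scores can identify.** Write a follow-up score as Y = B + L + M, where B is the pre-operative level, L the change due to the laparotomy and the course of the underlying disease, and M the change due to the mesh.

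- As planned, only Y is observed. B, L and M cannot be separated.
- With a baseline, Y − B = L + M. New or worse complaints can be told from pre-existing ones, but M is still mixed with L.
- Isolating M needs a comparator, which a single-arm study does not have.

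The impact wording in 11.8 therefore fails now, and a baseline alone would not rescue it.

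**4. Day 0 recall.** Let the score be taken h hours after incision. It is collected on the operative day, so h is below 24 and the 24-hour window contains 24 − h hours before incision. The documents do not give h. If h is assumed to lie between 2 and 12, then 22 to 12 of the 24 hours (92% to 50%) precede incision. That is how far the window reaches back, not a bias.

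The item asks for the worst pain, so the recorded value is max(P, Q), where P is the worst pre-operative pain in the window and Q the worst post-operative pain. It differs from Q only when P exceeds Q, and then by P − Q. The error can only raise the score. Its frequency and size depend on the joint distribution of P and Q, about which the documents say nothing.

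**5. Day 8 mode.** Set 11.7.4 beside 11.8. The first permits a phone call after discharge; the second describes a mark made by hand on a line. Neither document defines how a score is obtained by phone, and mode is not among the listed data items. Clinic and phone values would be summarised together at Day 8 in SAP 7.9.

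**The case against.** The best defence is that these endpoints are modest and descriptive. Pain is defined as pain after the operation at the surgical site, and no document says the VAS will show an effect of the mesh. The impact sentence covers only the survey, and the satisfaction half of that sentence needs no baseline. This stands: the Day 0 and Day 8 points bear on the quality of the pain data, not on the impact statement.

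A reader might infer that pre-operative pain generally contaminates the Day 0 score. The documents do not support that. A maximum changes only where pre-operative pain was the worse, and pain after a laparotomy may usually dominate.

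A reader might also infer that chronic pain cannot be assessed as a safety matter. That goes too far. Related pain has an adverse-event route: history is taken at screening (11.4), a pre-existing condition counts only if it worsened (13.1), and relatedness is judged separately for device, mesh placement and index procedure (13.4, 13.5.1). This route rests on history and judgment rather than a baseline score, but it exists.

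Two further reservations stand. The Club Hernie items are not shown, so some may have no pre-operative meaning. Protocol section 7 says the registry captures all pre-operative data, so a usable item may already exist, although none is scheduled or analysed. On the phone mode, the glossary defines the VAS more loosely as a 0-10 response scale; a spoken number is the likely practice but is not stated.

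**Conclusion.** The point holds in limited form. All three facts are in the text, and the SAP repairs none of them.

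- The follow-up scores describe post-operative levels and remain usable for that. They cannot separate new from pre-existing pain or impaired quality of life, and they do not support the impact wording in 11.8.
- The Day 0 item can record pre-operative pain in some subjects. How many cannot be computed from the documents.
- Sections 11.7.4 and 11.8 disagree on how a Day 8 score is obtained.

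Two of six secondary endpoints are affected. The primary endpoint, its sample size and patient satisfaction are not. It is tempting to count the subjects whose late pain would be misread, but that needs the prevalence of pre-operative pain and its persistence to 12 or 24 months, and the documents give neither. The conclusion assumes that no unscheduled registry item is in use as a baseline. The change is worth making because it is cheap, not because the main result is at risk.

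**What to change.** 1. **Baseline.** Add a VAS and those Club Hernie quality-of-life items that make sense before surgery to the screening column of protocol Table 2 and of the SAP section 5 schedule. In SAP 7.9, for subjects with a baseline, report change from baseline and the proportion with new or worse pain.
2. **Day 0 recall.** In protocol 11.7.1 and the synopsis, make the recall period run *since the end of surgery*.
3. **Day 8 mode.** Reconcile 11.7.4 with 11.8: define a verbal 0-10 scale for phone contacts, record the mode, and summarise Day 8 by mode.
4. **Wording.** In 11.8, describe the aim as *quality of life after surgery*. This is needed even with a baseline, because change from baseline cannot isolate the mesh without a comparator.

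The cost is a few minutes at a visit that already takes place, one extra data item for mode, and small text changes in both documents. The limitation is that subjects already enrolled have no baseline, so change scores would cover later enrollees only and the SAP should say so. If enrollment is too far advanced for item 1 to be useful, items 2 and 3 still help any assessments yet to come, and item 4 can be made at any time.
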